## 7.4 Clinical Laboratory Parameters

Clinical laboratory data including hematology and serum chemistry parameters will be entered into the electronic data capture (EDC) system and converted to International System (SI) units for analysis. Normal ranges will be merged in during dataset programming.

## 8 Data Handling

### 8.1 Imputation of Missing Data

#### 8.1.1 AE and Concomitant Medication Start and Stop Dates

**Start Date:** If only 'day' is missing, and the month and year are not the same as the month and year of the first dose, then day will be imputed with '01'. Otherwise, if the month and year are the same as first dose date, first dose date will be used. If 'day' and 'month' are missing, and 'year' is not missing, then month and day will be imputed with month and day of first dose date (assuming same 'year'). If year is not the same as first dose date, then Jan 1 will be imputed for the year provided. If the start date is completely missing, then the first dose date will be used. If the stop date is complete and the imputed start date is after the stop date, then the imputed start date will be set to the stop date. The original, non-imputed, dates will be retained in the clinical trial database and will be included in patient listings.

**Stop Date:** If only 'day' is missing, day will be imputed with last day of the month. If 'day' and 'month' are missing, and 'year' is not missing, then month will be imputed with '12' and day will be imputed with '31' (or date of study discontinuation/completion if earlier than 12-31 and year is the same as the year of discontinuation). If the stop date is completely missing, it will be set to the date of study discontinuation/completion. A stop date will not be applied to ongoing AEs. If the imputed stop date is greater than last the contact date, then the imputed stop date will be set to last contact date. The original, non-imputed, dates will be retained in the clinical trial database and will be included in patient listings.

#### 8.1.2 Missing normal ranges for laboratory parameters

No imputation will be applied to missing normal ranges.

## 9 Statistical Methods

All statistical analyses will be performed using SAS® Version 9.4 or higher, unless otherwise indicated.

Categorical variables will be summarized using counts and percentages. Percentages will be rounded to one decimal place except 100% will be displayed without any decimal places and percentages will not be displayed for zero counts.

Continuous variables will be summarized using the number of observations (n), mean, standard deviation, median, minimum, 25th and 75th percentiles, and maximum. The mean will be presented to one more and the standard deviation to 2 more decimal places than the precision of the original variable, while the quantiles will be presented at the same precision as the original variable.

All tables will be accompanied by corresponding listings.

### 9.1 Analysis Sets

Enrolled subjects are those subjects who have signed informed consent and met inclusion and exclusion criteria for either AIM-HN or SEQ-HN.

Subjects enrolled in AIM-HN fall under one of two analysis populations of interest:

High VAF = VAF >= 20% at screening

All VAF = Low VAF and High VAF or all subjects

### 9.1.1 Modified Intent-to-Treat (mITT) Analysis Set

The mITT analysis set consists of all subjects in the AIM-HN who received at least one dose of tipifarnib.

The analysis set will be used for all the efficacy analyses.

### 9.1.2 Per Protocol Analysis Set (PPS)

The PPS consists of all subjects in the AIM-HN who received at least one dose of tipifarnib, have confirmed measurable disease at baseline per RECIST v1.1 by IRF, have at least one post baseline efficacy assessment, and do not have any major protocol deviation that will impact the study outcome.

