To participate in AIM-HN, all subjects must have measurable disease that meets the criteria for selection as a target lesion according to Response Evaluation Criteria in Solid Tumors (RECIST) v1.1. The presence of at least one measurable target lesion per RECIST v1.1 must be confirmed by local radiology prior to enrollment. Subjects without at least one measurable target lesion confirmed by local radiology will not be enrolled into AIM-HN.

HNSCC diagnosis by local site pathology laboratory will be used; however, all subjects must provide pathology material for central pathology review. Central confirmation of pathological diagnosis of HNSCC will be required for inclusion of subjects in the per-protocol analysis set. Subjects in whom a diagnosis of HNSCC is not confirmed by central review may continue to receive study treatment and will be included in the modified intent-to-treat (mITT) analysis set.

All AIM-HN enrolled subjects must have a known missense HRAS tumor mutation based on centralized testing or other HRAS test used by the trial site that has been approved by the Sponsor. HRAS status should be assessed on tumor obtained subsequent to the most recent prior therapy in order to obtain the most recent tumor biology; if tumor tissue that does not meet this criterion must be used (e.g. risk of biopsy is too high, patient refuses new biopsy), the investigator should document the reason. If several samples are available, HRAS testing should be performed in the most recently obtained tumor sample. To facilitate development of appropriate diagnostic testing, all subjects must provide enough tumor material for confirmation of HRAS status by central lab. This tissue should be from the same source as that used for pre-screening, or the reason that is not possible documented. Subjects who were enrolled in the study based on HRAS mutation using a Sponsor approved test, but in whom a missense HRAS mutation is not confirmed by central laboratory, may continue to receive study treatment. SEQ-HN subjects who were initially identified as wild type HRAS but in whom an HRAS mutation is later detected during the course of their standard therapy, will become eligible to screen for AIM-HN.

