An overview of the AIM-HN sub-study design is shown in [Figure 2](#).

Figure 2: AIM-HN Design

[figure not shown]
- **SEQ-HN**

SEQ-HN is an observational sub-study [REDACTED] Demographics, disease history, information on prior anti-cancer treatments and outcomes to prior treatments for HNSCC will be collected from all enrolled subjects. At least approximately 225 control patients

with HNSCC without known HRAS mutations, will be enrolled into SEQ-HN. As part of their participation in SEQ-HN, patients will be followed up through initiation of second line therapies, death or consent withdraw, whichever occurs first. A subset of the approximate 225 control patients will be matched to the HRAS mutant subjects to the greatest extent possible according to pre-defined patient characteristics. If necessary, additional follow up of the matched HRAS wildtype HNSCC patients enrolled into SEQ-HN may continue until all AIM-HN objectives are completed and KO-TIP-007 end of study is reached. Control patients with HNSCC with wildtype HRAS will not receive tipifarnib treatment as part of their participation in SEQ-HN; however, they may be compensated for their participation in data collection, blood sampling, screening and follow up procedures according to institutional guidelines.

An overview of the SEQ-HN design is shown in [Figure 3](#).

Figure 3: SEQ-HN Design

NUMBER OF SUBJECTS PLANNED:

In AIM-HN, at least 80 subjects meeting all criteria for inclusion in the per-protocol analysis set will be enrolled.

Subject criteria for inclusion in the per-protocol analysis set include: received at least one dose of tipifarnib, confirmed measurable disease at baseline per RECIST v1.1 by IRF, confirmed diagnosis of HNSCC by central pathology review, and at least one post baseline disease assessment (e.g. tumor assessment visit). In SEQ-HN, approximately an additional 225 patients with HNSCC but without detected HRAS mutations will also be enrolled. A subset of the wildtype HRAS subjects will be selected as a matched-control subset to those subjects with:

- HRAS mutant tumors enrolled as part of AIM-HN,

- HRAS mutant tumors that do not enroll in AIM-HN, but have 1L data collected during the pre-screening period

SUBJECT SELECTION:

Inclusion Criteria: AIM-HN

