**Figure 2: AIM-HN Design**

All subjects must have measurable disease that meets the criteria for selection as a target lesion according to RECIST v1.1 and presence of at least measurable target lesion by local radiology prior to enrollment is required. HNSCC diagnosis will be by local laboratory. All AIM-HN enrolled subjects must have a known missense HRAS tumor mutation based on centralized testing or other HRAS test used by the trial site that has been approved by Kura Oncology, Inc.

AIM-HN enrolled subjects will receive treatment with tipifarnib until disease progression, unacceptable toxicity or any criteria for withdrawal from the trial or treatment occurs. Tipifarnib will be administered with food at a starting dose of 600 mg, orally, bid on days 1-7 and 15-21 of 28-day treatment cycles. Stepwise 300 mg dose reductions to control treatment-related, treatment-emergent toxicities may occur.

Tumor assessment for the primary analysis will be performed by IRF according to RECIST v1.1 and provided to the IDMB. Investigator assessment of tumor response will also be collected and reported as a supportive analysis. Tumor response assessment should occur approximately every 8 weeks ( $\pm 5$  days) for the first 12 months; thereafter, tumor response assessment should occur approximately every 12 weeks ( $\pm 5$  days) until disease progression. The tumor response assessment schedule (every 8-12 weeks) should be maintained regardless of dosing delays or additional imaging assessments performed. Upon disease progression, all subjects will be followed approximately every 12 weeks for survival and the use of subsequent therapy until either death or End of Study (up to 2 years after the enrollment of the last study subject, see [protocol Section 6.7.1](#)), whichever occurs first. All subjects will be followed-up for safety through the End of Treatment visit which occurs approximately 30 days after treatment discontinuation or immediately before the administration of another anticancer treatment, whichever occurs first. Additional safety follow-up may be conducted if unresolved toxicity is present at this End of Treatment visit.

[figure not shown]

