## 9.3 Important Protocol Deviations

Protocol deviations will be identified, including but not limited to, subjects that were enrolled even though they did not meet all eligibility criteria, subjects who took concomitant medications specifically prohibited by the protocol, and subjects who received the wrong study drug or incorrect dose. The reason for each protocol deviation will also be identified.

Per PRA processes, important protocol deviations data will be entered into our Clinical Trials Management System (CTMS). The study team and the sponsor will conduct on-going reviews of the deviation data from CTMS and the resulting set of per-protocol subjects throughout the study, adjusting the deviation criteria as appropriate. The PPS must be finalized at the post-freeze data review meeting (or earlier), prior to database lock.

Important protocol deviations for mITT in the AIM-HN and all enrolled subjects in the SEQ-HN will be summarized by deviation category. All the protocol deviations, including the protocol deviations related to COVID-19 effect on study assessments, will be listed. Data listings will present protocol deviations by subject.

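### The visible SAP per-protocol set omits the protocol's central pathology criterion and adds an unlisted, adjustable deviation exclusion, so the named sensitivity population no longer checks robustness to unconfirmed histology

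*SAP*

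**What the plan says.** **Protocol.** The synopsis (Study Design, AIM-HN) states: "Central confirmation of pathological diagnosis of HNSCC will be required for inclusion of subjects in the per-protocol analysis set". Under Number of Subjects Planned it lists four criteria for the set: at least one dose of tipifarnib, measurable disease confirmed by the independent review facility (IRF), "confirmed diagnosis of HNSCC by central pathology review, and at least one post baseline disease assessment". Section 6.2.1 repeats the pathology requirement. Subjects whose diagnosis is not confirmed centrally may stay on treatment and remain in the mITT set. The visible list has no deviation criterion.

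**SAP.** Section 9.1.2 keeps the dosing requirement and asks that subjects "have confirmed measurable disease at baseline per RECIST v1.1 by IRF". It ends with the requirement that they "have at least one post baseline efficacy assessment, and do not have any major protocol deviation that will impact the study outcome". Central pathology does not appear in the visible SAP; the design text in section 5.1 says only "HNSCC diagnosis will be by local laboratory".

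Section 9.3 has the study team and the sponsor conduct "on-going reviews of the deviation data from CTMS and the resulting set of per-protocol subjects throughout the study, adjusting the deviation criteria as appropriate". It also sets a limit: "The PPS must be finalized at the post-freeze data review meeting (or earlier), prior to database lock". Section 9.7 places the sensitivity efficacy analyses in this set.

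**The concern.** Keeping unconfirmed tumours in mITT while removing them from the per-protocol set gives the protocol a built-in contrast. If the two response rates agree, misdiagnosed tumours are not driving the result. The visible SAP loses that contrast.

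The added criterion raises a separate problem. Whether a deviation will affect the outcome is a judgement. The rules for that judgement may change during the study, the trial is open label, and no visible text keeps response data from those who make it. Exclusions decided in that setting can lean towards non-responders. Agreement between the per-protocol and mITT results would then be weaker evidence than it looks.

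**Working it through.** No stated figure decides a question about a definition, so the first step sets the two definitions side by side.

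| Criterion | Protocol synopsis | SAP 9.1.2 |
|---|---|---|
| At least one dose | yes | yes |
| IRF-confirmed measurable disease at baseline | yes | yes |
| At least one post-baseline assessment | yes | yes |
| HNSCC confirmed by central pathology | yes | absent |
| No major deviation affecting outcome | not in the visible list | added, not itemised |

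Three of four criteria are kept, one is dropped and one is added. SAP 9.3 gives open-ended examples of deviations (eligibility failures, prohibited medication, wrong drug or dose). It calls them important, whereas 9.1.2 speaks of major ones, and neither section says which of them exclude a subject.

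**Inputs for the size.** The protocol synopsis gives a planned N of at least 80, a hypothesised response rate p1 = 30%, an uninteresting rate p0 = 15% and a 2-sided 95% interval. The share not confirmed centrally is not given; 0-10% is assumed. Using 80 as the denominator is illustrative: the primary population is the high-VAF subset, and the SAP mentions early closure.

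**Set size.** 80 × 0.05 = 4 and 80 × 0.10 = 8, so restoring the criterion would leave 80 down to 72 subjects.

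**Response rate, starting from 24/80 = 30.0%.** With m subjects removed, the rate lies between (24 − m)/(80 − m), if all were responders, and 24/(80 − m), if none were.
- m = 4: 20/76 = 26.3% to 24/76 = 31.6%.
- m = 8: 16/72 = 22.2% to 24/72 = 33.3%.

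**Exact lower 95% limits** (Clopper-Pearson: the 0.025 quantile of a Beta distribution with parameters x and n − x + 1).
- 24/80: 20.3%. Removing only non-responders gives 24/76: 21.4%, and 24/72: 22.7%. All stay above 15%.
- Removing only responders gives 20/76: 16.9%, and 16/72: 13.3%. The last needs all eight unconfirmed subjects to be responders.

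**Near the boundary.**
- Histology: 20/80 has a lower limit of 16.0%. If two responders prove unconfirmed, 18/78 = 23.1% has a lower limit of 14.3%.
- Deviations: 19/80 has a lower limit of 14.95%. Excluding four non-responders gives 19/76 = 25.0%, with a lower limit of 15.8%.

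The plan attaches no decision rule to the per-protocol interval. Reading it against 15% is by analogy with the primary analysis.

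**The case against.** Several points on the other side stand.

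- **The set keeps most of its purpose.** A reader might infer that it no longer tests what it was built to test. Three of the four criteria remain, so it still checks dependence on IRF-measurable disease and on having a post-baseline assessment. Only the histology check is lost.
- **Outcome-driven selection is not shown.** A reader might infer that the sponsor picks subjects with responses in view. The text describes review of deviation data by the study team and the sponsor together, with the set final before lock. IRF readings go to the monitoring board, and no visible text says the deviation reviewers see them. The pre-lock freeze rules out selection after lock. What remains is a possibility: the trial is open label, investigators assess response locally, and no barrier is stated.
- **The change may be recorded.** The items before number 4 in SAP section 3 are redacted, as is part of protocol section 12.2.1. Nobody can say from these documents that the change is undisclosed, or that the protocol has no deviation criterion at all.
- **Some refuted diagnoses might still leave the set.** Non-squamous and certain other histologies are exclusions, and eligibility failures count as deviations. But enrolment on local diagnosis is allowed, and no visible text treats failed central confirmation as a major deviation.
- **The planned 80.** A reader might infer that the 80 counted in the protocol are not the 80 analysed in the SAP. The visible SAP plans no analysis of 80 AIM-HN subjects and reports early closure, so that does not follow.

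Investigator-assessed response and the protocol's missing-data and VAF cut-point analyses give further support, but none of them tests histology.

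**Conclusion.** The conflict is real and limited. As visibly written, the SAP's sensitivity population differs from the protocol's by one dropped criterion and one unspecified, adjustable addition. It cannot show whether the result is robust to unconfirmed histology, and its membership is open to influence from known responses. The documents do not show that such influence occurs.

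The primary high-VAF response rate uses mITT and does not change. Under the assumed 0-10% non-confirmation, 0 to 8 of 80 subjects are affected. With 30% observed response and four removed, the sensitivity rate moves by −3.7 to +1.6 percentage points, and the lower limit stays above 15%. Conclusions drawn from the sensitivity analysis could change in near-boundary results or in the extreme case of eight unconfirmed responders. The point should be corrected before lock, but it does not threaten the primary analysis.

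**What to change.** - **SAP 9.1.2:** restore central pathology confirmation of HNSCC as a criterion, and say how a missing or inadequate central result is handled. Tissue for central review is required of every subject, but the documents do not show that a result exists for each. If the omission was intended, state and justify it, and add a sensitivity analysis limited to centrally confirmed subjects.
- **SAP 9.3:** replace "adjusting the deviation criteria as appropriate" with a fixed list of the deviations that exclude a subject, set before lock and applied by people without access to response data. Use one term for these deviations in 9.1.2 and 9.3.

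The cost is SAP wording and a check of the central pathology results. The per-protocol set may be a few subjects smaller (0-8 of 80 under the assumed range), with a slightly wider interval.

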### 9.1.3 Safety Analysis Set (SAS)

The SAS consists of all subjects in the AIM-HN who received at least one dose of tipifarnib.

The analysis set will be used for the analyses of safety.

## 9.2 Subject Disposition

The count and percentage of subjects pre-screened, screened, enrolled and treated in the AIM-HN of the study will be presented, along with the count and percentage of subjects with high VAF and subjects included in each analysis set defined in [Section 9.1](#). The count of subjects who discontinue the study along with a breakdown of the corresponding reasons for discontinuation will also be summarized for subjects enrolled in AIM-HN and subjects enrolled in SEQ-HN. A similar summary will be presented for subjects discontinuing study treatment in the AIM-HN safety analysis set.

## 9.3 Important Protocol Deviations

Protocol deviations will be identified, including but not limited to, subjects that were enrolled even though they did not meet all eligibility criteria, subjects who took concomitant medications specifically prohibited by the protocol, and subjects who received the wrong study drug or incorrect dose. The reason for each protocol deviation will also be identified.

Per PRA processes, important protocol deviations data will be entered into our Clinical Trials Management System (CTMS). The study team and the sponsor will conduct on-going reviews of the deviation data from CTMS and the resulting set of per-protocol subjects throughout the study, adjusting the deviation criteria as appropriate. The PPS must be finalized at the post-freeze data review meeting (or earlier), prior to database lock.

Important protocol deviations for mITT in the AIM-HN and all enrolled subjects in the SEQ-HN will be summarized by deviation category. All the protocol deviations, including the protocol deviations related to COVID-19 effect on study assessments, will be listed. Data listings will present protocol deviations by subject.

## 9.4 Extent of Study Drug Exposure

Exposure to study drug will be summarized in the AIM-HN safety analysis set. Descriptive statistics will be provided for duration of exposure, the total number of cycles initiated, actual cumulative dose administered, and Relative Dose Intensity.

The count and percentage of subjects with at least 1 dose interruption and at least 1 dose decreased per protocol will be presented along with a summary of the reasons for dose interruptions and dose decrease.

A listing of tipifarnib exposure will also be created.

## 9.5 Prior and Concomitant Medications

Using the AIM-HN safety analysis set, the count and percentage of subjects using at least one medication along with the count and percentage of subjects using at least one medication for each PT.

All medications will also be listed. In the listing, medications will be classified as prior or concomitant.

## 9.6 Demographic and Baseline Disease Characteristics

Demographics including age (years) at treatment start date, sex, race, ethnicity, height (cm) and weight (kg) will be summarized in the AIM-HN mITT analysis set, and AIM-HN PPS.

The following baseline characteristics will be summarized in AIM-HN mITT analysis set:

HRAS mutation type

Months from diagnosis of metastatic disease to first dose of tipifarnib, i.e., (first dose date – date metastatic disease first diagnosed + 1)/30.4375.

Disease history at primary diagnosis

Anatomical disease site of primary tumor

Disease stage

Tumor, node, and metastasis stage

Histologic grade

Anti-cancer systemic treatment for HNSCC

Prior lines of therapy

Setting, type, anatomical site, performance status, best response, and treatment outcome response criteria for first line of therapy

Best response, and treatment outcome response criteria for last line of therapy prior to screening

Anti-cancer surgery for HNSCC

Radiological treatment for HNSCC

Anatomical Site

Treatment Intent

Radiation Therapy Type

HPV status (positive/negative)

Substance abuse (Tobacco/Alcohol/Betel nut)

